Current exposure to study treatment (as-treated analysis)	Indicator of current use of empagliflozin, or a DPP-4 inhibitor, either alone or as a combination.	Time-dependent
Exposure to Empagliflozin (Intention-to-treat)	Drug purchased/prescribed at index date, which is one of empagliflozin, or a DPP-4 inhibitor.	Fixed at index date
Cumulative dosage of empagliflozin use	Time-dependent cumulative sum of drug consumption based on the daily defined dosage of empagliflozin since entry into the study cohort.	Time-dependent
Daily dosage of empagliflozin per use	The dosage of empagliflozin prescribed per daily use (10mg vs 25mg).	Time-dependent
Time since first dose of empagliflozin	Time-dependent cumulative sum of duration since the first use of (exposure to) empagliflozin.	Time-dependent
Treatment complexity	Monotherapy, dual combination therapy, or triple combination therapy (based on predefined groups).	Fixed at index date
Switch	Switch from the drug purchased/prescribed on index date to any other drug in the primary exposure.	Time-dependent
Concomitant use of insulin	Was empagliflozin an add-on to insulin (yes/no).	Fixed at index date
Concomitant use of metformin	Was empagliflozin an add-on to metformin (yes/no).	Fixed at index date
Concomitant use of metformin	Concomitant use of metformin either as fixed-dose combination or free combination.	Time-dependent
Ever used other oral glucose lowering medication	Use of other oral glucose lowering drugs based on predefined drug groups in the past.	Time-dependent
Ever used metformin	Was metformin ever used – taking value 'yes' as soon as one prescription with metformin is purchased.	Time-dependent

Exposure definition	Description	Time-dependent or Fixed at index date
Ever used sulphonylureas	Was sulphonylureas ever used – taking value ‘yes’ as soon as one prescription with sulphonylureas is purchased.	Time-dependent
Ever used thiazolidinediones	Was thiazolidinediones ever used – taking value ‘yes’ as soon as one prescription with thiazolidinediones is purchased.	Time-dependent
Ever used GLP-1	Was GLP-1 ever used – taking value ‘yes’ as soon as one prescription with GLP-1 is purchased.	Time-dependent
Ever used insulin	Was insulin ever used – taking value ‘yes’ as soon as one prescription with insulin is purchased.	Time-dependent

GLP=glucagon-like peptide

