8.3.5 Follow-up time

For the primary AT analyses, the follow-up time (time at risk) will begin 6 months after the index date (lag period to account for empirical induction/promotion period of cancer) and end at urinary tract (bladder, renal or other) cancer or at any of the censoring events including discontinuation of index drug treatment.

For the sensitivity ITT analyses, the follow-up time will begin 6 months after the index date and end at urinary tract (bladder, renal or other) cancer or any of the censoring events excluding treatment discontinuation of index drug.

Patients with censored follow-up time will not be able to re-enter study cohort at a later time point. Follow-up will not be censored if oral or injectable glucose lowering drugs other than the index drugs are prescribed in addition to empagliflozin, a DPP-4 inhibitor, or a SGLT-2 inhibitor after the index date.

The lag period of 6 months is to account for an empirical induction/promotion period. Information in the first 6 months after the index date (i.e., first 6 months of follow-up) will be excluded, including patients with less than 6 months of follow-up and all occurrences of cancer within the first 6 months of follow-up, in order to consider a biologically meaningful induction/promotion time window. Sensitivity analyses will expand the lag period to 12 months.

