4. RESEARCH METHODS

4.1. STUDY DESIGN

This is a non-interventional, comparative, cohort safety study based on European healthcare databases and includes databases from the UK, Sweden and Finland. The databases for this study are constructed from linked prescription, hospital, general practitioner, cancer and death registration records.

The study will use an “incident users” design and compare new users of empagliflozin to new users of DPP-4 inhibitors. The index date will be defined as the date on which each identified new user receives the index prescription for empagliflozin, or a DPP-4 inhibitor.

To minimize channelling bias, individuals will be matched with similar treatment and clinical history at index date by deriving propensity scores (PS) conditional on factors affecting the treatment and outcome [1], [2]. Propensity-score-matched cohorts will be derived from the study base by matching patients who initiate empagliflozin with patients who initiate DPP-4 inhibitors at index date with the highest possible matching ratio (1:1, 1:2, or 1:3 using Greedy matching methods).

Depending on sample size, combination exposures with metformin will be accounted for through separate PS, stratification, or adjustment. Additional analyses will explore the presence of detection/diagnostic bias as screening for urinary tract signs or symptoms may be more frequently among empagliflozin users. The potential for diagnostic bias will be evaluated and addressed through consideration of the frequency of urine dipstick testing (as captured through albuminuria tests) and stage of cancer at the time of diagnosis (as more early-stage cancers in one group would be suggestive of diagnostic bias).

The primary, secondary, and further analyses utilize a cohort design which will allow direct estimation of the IRs and aHRs of multiple outcomes of interest among new users of empagliflozin compared with new users of a DPP-4 inhibitor. The covariate information will be assessed during the time preceding treatment initiation (varying length look-back (pre-index) period) and during follow-up and will include all historical information available for each patient up until occurrence of outcome or censoring. Follow-up will start 6 months after the index date (12 months in sensitivity analyses) to account for an empirical induction/promotion period.

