5.1.3. EXPOSURE TIME

Time at risk will start on index date and continue until first treatment discontinuation (see definition in Section 5.1.6). Continuous exposure will be defined as successive exposure periods for the study drugs separated by gaps of 30 days at most. Duration of exposure

Proprietary confidential information © 2024 Boehringer Ingelheim International GmbH or one or more of its affiliated companies

episodes for individual prescriptions of study drugs will be derived based on package size, unit strength and daily dose.

To account for an empirical induction/promotion period of cancer, a latency period of 6 months (180 days) after the index date is applied. Patients with less than 6 months (180 days) of follow-up time will be excluded. In addition, patients with any diagnosis of any cancer within the latency period will be excluded. In a sensitivity analysis, the latency period will be extended to 12 months (365 days).

* Other drugs: a prescription of another drug (empagliflozin, a DPP-4 inhibitor, or a SGLT-2 inhibitor) other than index drug

Figure 1 Definition of continuous exposure period of index drug

For the primary AT analyses, the time at risk will begin after the latency period and end at urinary tract (bladder, renal or other) cancer or at any of the censoring events (listed in Table 4), whichever occurs first. In addition, treatment discontinuation of the index drug (defined in Section 5.1.6) is an additional censoring variable.

For the sensitivity ITT analyses, the time at risk will begin after the latency period and end at urinary tract (bladder, renal or other) cancer or any of the censoring events excluding treatment discontinuation of the index drug.

Patients with censored time at risk will not be able to re-enter the study cohort at a later time point. The time at risk will not be censored if oral or injectable glucose-lowering drugs other than the index drugs and SGLT-2 inhibitors are prescribed in addition to empagliflozin or a DPP-4 inhibitor after the index date.

Proprietary confidential information © 2024 Boehringer Ingelheim International GmbH or one or more of its affiliated companies

Table 4 Censoring events.

Censoring event	Definition	Data source
All-cause mortality	Censoring of follow-up time occurs at the date of death regardless of the cause. Applied in all analyses.	UK: CPRD-GOLD and Aurum Sweden: Cause of death register Finland: Cause of death register

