5.1.8. SECONDARY EXPOSURE DEFINITIONS

Exposure definitions based on dosage or duration

Table 6 Exposure definitions based on dosage or duration

Exposure	Definition	Details	Data source
Cumulative dose of empagliflozin use in grams	Time-updating cumulative sum of empagliflozin dose consumption based on the daily prescribed dose and purchased amounts since the start of follow-up. ATC codes for empagliflozin in Annex II.	Time-dependent Categorical ¹ : Never 0 - <cumulative dose Q1 ≥ Q1 to < Q2 ≥ Q2 to < Q3 ≥ Q3	UK: CPRD Sweden: SPDR Finland: FPR
Daily dose of empagliflozin	The dosage of empagliflozin prescribed per daily use (10mg vs. 25mg). ATC codes for empagliflozin in Annex II.	Time-dependent Categorical: Never 10 mg 25 mg	UK: CPRD Sweden: SPDR Finland: FPR
Updating from index date onwards.*			

Proprietary confidential information © 2024 Boehringer Ingelheim International GmbH or one or more of its affiliated companies

Cumulative exposure duration to empagliflozin in months	Time-updating cumulative sum of duration since the first use of empagliflozin (alone or in combination with metformin), in months. ATC codes for empagliflozin in Annex II.	Time-dependent Categorical ² : Never 0 - < cumulative duration Q1 Updating from index date onwards.* ≥ Q1 to < Q2 ≥ Q2 to < Q3 ≥ Q3	UK: CPRD Sweden: SPDR Finland: FPR
---	--	--	--

*The last observed value will be carried forward for 3 months (90 days) to account for the 90-day delay between end of treatment and treatment discontinuation as defined in Section 5.1.6.

¹ The categories are defined based on the quartiles of overall cumulative dose (grams) of the study population

² The categories are defined based on the quartiles of overall cumulative exposure duration (months) of the study population

Intention-to-treat exposure definition

The intention to treat exposure definition assumes that individuals do not discontinue the treatment of an index drug.

Table 7 Intention-to-treat exposure definition

Exposure	Definition	Details	Data source
Exposure to index drugs (Intention to treat)	Purchase of empagliflozin (alone or in combination with metformin) or any DPP-4 inhibitors (including combinations). ATC codes for empagliflozin and DPP-4 inhibitors in Annex II.	Time-fixed Categorical: Empagliflozin	UK: CPRD Sweden: SPDR Finland: FPR

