6.3. METHODS ADDRESSING BIAS

Potential biases will be addressed as follows:

- Selection bias and immortal time bias is addressed thru the study design. It include a new user cohort design, a selection of comparator drugs with the same indication and prescribed to patients with potentially similar T2D disease severity, and a definition of exposure and study entry based on information before or at index date.
- Channeling bias is addressed by using propensity score matching to construct balanced exposure groups. In addition, the year of the index date (date of first prescription of the study group) is used as an exact matching criteria.
- Bias due to definitions of exposure, definition of follow-up times and other relevant covariates will be addressed through sensitivity analyses.

Proprietary confidential information © 2024 Boehringer Ingelheim International GmbH or one or more of its affiliated companies

- Diagnostic bias will be evaluated and addressed in sensitivity analyses through consideration of the frequency of urine dipstick testing (as captured through albuminuria tests) and stage of cancer at the time of diagnosis (as more early-stage cancers in one group would be suggestive of diagnostic bias).

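### SAP Table 6 counts cumulative empagliflozin dose from the start of follow-up, which as explicitly defined leaves out the first 180 days of dose that the protocol counts

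*SAP*

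**What the plan says.** The cumulative-dose variable is defined differently in the two documents.

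- SAP 5.1.8, Table 6, cumulative dose in grams: "Time-updating cumulative sum of empagliflozin dose consumption based on the daily prescribed dose and purchased amounts since the start of follow-up". The categories are a never-exposed group plus quartiles of cumulative grams.
- Protocol 8.3.1, Table 3, the same variable: "Time-dependent cumulative sum of drug consumption based on the daily defined dosage of empagliflozin since entry into the study cohort". (The two also differ in the dose unit, which is a separate matter.)
- SAP Table 6, cumulative duration: "Time-updating cumulative sum of duration since the first use of empagliflozin (alone or in combination with metformin), in months". This row is updated from the index date, as is the daily-dose row.

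The start of follow-up is defined explicitly in both documents. SAP 4.1: "Follow-up will start 6 months after the index date (12 months in sensitivity analyses) to account for an empirical induction/promotion period". Protocol 8.3.5, for the primary analysis: "the follow-up time (time at risk) will begin 6 months after the index date". SAP 5.1.3 fixes the length: "a latency period of 6 months (180 days) after the index date is applied".

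**The concern.** Put together, the SAP's definition of cumulative dose and its definition of follow-up start the gram count at day 180. A patient who has taken empagliflozin for six months would then enter the risk period with zero grams on the dose clock and about six months on the duration clock. The protocol's variable would already hold the dose taken since cohort entry.

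At stake is secondary objective (a), the hazard ratio by increasing cumulative dose. If the omitted amount differs between patients, some of them fall into a different gram quartile and the dose-response gradient is estimated on a different ordering. Even if the order is unchanged, the reported cut-points in grams would not describe the dose actually taken. And if the term can be read two ways, programmers working on separate country datasets could build different variables that are then pooled.

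**Working it through.** Neither document states a gram figure, so there is nothing to reproduce. The check compares the time origins and then does direct arithmetic.

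**Inputs.** Lag of 180 days (SAP 5.1.3). Daily dose of 10 mg or 25 mg (SAP Table 6). Expected mean follow-up of 2.2 years in Sweden and 2.4 years in the UK and Finland (protocol 8.5).

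**1. Origins side by side.**

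| Variable | Origin stated | Day from index, explicit definitions |
|---|---|---|
| Cumulative dose, SAP Table 6 | start of follow-up | 180 |
| Cumulative dose, protocol Table 3 | cohort entry | 0 |
| Cumulative duration, SAP Table 6 | first use | 0 |

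That cohort entry is the index date is an inference. SAP 6.3 refers to "a definition of exposure and study entry based on information before or at index date", and protocol Annex 4 labels as fixed at cohort entry what protocol Table 3 labels as fixed at index.

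**2. Grams omitted** = daily dose × 180 / 1000.

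- 10 mg: 10 × 180 / 1000 = 1.8 g.
- 25 mg from day 1: 25 × 180 / 1000 = 4.5 g.
- 10 mg, then 25 mg from day s: (10s + 25(180 − s)) / 1000. This gives 4.05 g for s = 30, 3.15 g for s = 90 and 1.8 g for s = 180.

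**3. Share of total dose omitted**, for constant use over the stated mean follow-up. The daily dose cancels, so the share is the same at both strengths.

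- Mean counted after the lag: 180 / (2.2 × 365.25 + 180) = 18.3%; 180 / (2.4 × 365.25 + 180) = 17.0%.
- Mean counted from index: 180 / (2.2 × 365.25) = 22.4%; 180 / (2.4 × 365.25) = 20.5%.

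The first pair matches the definition under which dose is lost. Both are shares at the mean follow-up, not the mean of individual shares.

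**4. Does the order change?** If everyone takes the same dose in the first 180 days, the same amount is subtracted from each. Ranks then stay as they were, and so does quartile membership when the cut-points use the same clock. If dose differs in that period, ranks can reverse:

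- 10 mg for 900 days: 9.0 g from index; 10 × 720 / 1000 = 7.2 g from day 180.
- 25 mg for 400 days: 10.0 g from index; 25 × 220 / 1000 = 5.5 g from day 180.

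**5. Illustration under assumptions that are not in the documents.** Take a constant dose from day 1 and an exponential time on treatment after day 180 with mean 1.8 years, capped at 2,160 days. With 20%, 50% or 80% of users on 25 mg, about 12%, 18% or 10% of users change quartile. With a single strength, none do.

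**The case against.** The strongest reply is that no dose is lost, because follow-up here means time since index. Several places use it that way:

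- SAP 5.1.3 excludes patients with under 180 days of follow-up.
- Protocol 8.3.5 itself calls the first six months after index the first six months of follow-up.
- The title of SAP Table 21 removes cancers within six months of index from those found in follow-up, which would be redundant if follow-up began at day 180.
- Protocol Annex 5 censors on other SGLT-2 use from the start of follow-up, which would ignore early switches if that start were day 180.
- The protocol abstract places the index date itself within follow-up.

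Table 6 is also broken in the available text. The note about updating from the index date is visible for the daily-dose and duration rows. Whether it also belonged to the cumulative-dose row cannot be told.

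This stands as far as it goes. A reader might infer that the SAP certainly discards six months of dose, and the documents do not support that. They show that the only explicit definition gives that result, while looser usage gives another.

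Three further inferences also fail:

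- **That 25 mg users suffer a bias 2.5 times larger.** The factor is only 25/10. It needs 25 mg from day 1, whereas protocol section 6 describes starting at 10 mg with a possible later increase, and the proportional loss is equal for equal duration.
- **That the plan treats the earliest dose as the most relevant.** The documents say only that the lag covers an empirical induction or promotion period and that early cancers are excluded.
- **That the dose-response result is known to be misranked.** The share of patients on 25 mg during the lag is not given.

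The SAP also cites protocol version 6.0, whose wording is not available; the protocol supplied is version 8.0.

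**Conclusion.** The point holds as a conflict of definitions with a conditional loss. On the explicit definition of follow-up, SAP Table 6 departs from protocol Table 3 and from its own duration row by 180 days. Nothing in either document gives a reason for the difference. The SAP change log records adjustments to time at risk, latency and discontinuation, and in general terms that drug-exposure algorithms were specified, but no change of origin for cumulative dose.

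The size rests on unbroken use through the lag and on the stated mean follow-up applying to empagliflozin users. The effect on ranks, and so on the dose-response hazard ratios, cannot be sized from the documents. It is nil if all patients take one strength in the first 180 days.

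The scope is narrow: the cumulative-dose hazard ratios and incidence rates (SAP Tables 26 and 30) and their pooled versions. The primary as-treated hazard ratios, the duration and daily-dose analyses and the power calculations are not affected. The wording should still be settled before the analysis is run, because it defines the exposure for a stated secondary objective.

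**What to change.** In the cumulative-dose row of SAP Table 6, replace the start-of-follow-up origin with: *since the index date (first empagliflozin prescription/dispensing)*. Patients then enter the risk period at day 180 carrying the dose already accrued. Derive the quartile cut-points on the same clock. Name the index date itself rather than substituting time at risk, since SAP 5.1.3 uses that term both from index and from the end of the latency period.

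The cost is one phrase and the matching line of code. No new data are needed: SAP 5.1.7 already builds exposure from the index date, so the prescriptions for the first 180 days are in hand. The layouts of Tables 26 and 30 do not change.

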8.2.5 Inclusion and exclusion criteria

The study population will be selected from the broad study population with the following inclusion and exclusion criteria:

Inclusion criteria:

- Diagnosis of T2D

- To identify the diagnosis in the UK, lists of codes that have been previously used to identify patients with T2D in the CPRD [[P14-16383](#)] will be utilized ([Annex 3](#)).
- For Swedish registers, identification of diabetes will be based on prescription records and the National Diabetes Register; all non-T2D patients will be excluded. The final algorithm to identify patients with T2D in each data source, which might include medication codes and glucose/glycated haemoglobin test results, will be described in the statistical/epidemiological analysis plan (SEAP).
- In Finnish registers, identification of patients with T2D will be based on prescription records and diagnoses available in various data sources; all non-T2D patients will be excluded. More specifically, all persons with dispensations of empagliflozin, or a DPP-4 inhibitor will be identified. Patients with non-T2D will be identified with the following criteria: special reimbursement of diabetes drugs with an ICD-10 diagnosis for a non-T2D, type 1 diabetes mellitus (T1D), pre-existing T1D before pregnancy, gestational diabetes, malnutrition-related to diabetes mellitus, neonatal diabetes mellitus, other specified diabetes mellitus, diabetes mellitus due to underlying condition, and drug- or chemical-induced diabetes mellitus. The specific diagnosis codes will be included in the SEAP.
- Age over 18 years at index date.
- At least 1 year of membership in the medication database prior to index date; in CPRD, at least 1 year of continuous up-to-standard registration in the CPRD prior to the index date.
 - This is the minimum look-back period and is informative of the history of treatments and other medical conditions in the recent past. Some of the important covariates to be accounted for in matching at index date are derived from the look-back period.

Exclusion criteria:

- Patients with any cancer (excluding non-melanoma skin cancer) recorded at any time prior to the index date (i.e., during the available look-back time).
- Diagnosis of T1D or other specific non-T2D.
- Use of any SGLT-2 inhibitor or any DPP-4 inhibitor (including free and fixed-dose combinations) recorded at any time prior to index date (i.e., during the available look-back time).

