8.5 STUDY SIZE

The study size will be driven by the uptake of empagliflozin and the primary comparator (DPP-4 inhibitors) in the UK, Sweden, and Finland. Originally, it was expected that by the end of 2019, approximately 18,000 empagliflozin-treated patients will accumulate in the CPRD and Swedish databases. However, based on the conservative estimates from the fifth interim analysis ([Annex 1](#)), the expected sample size is higher than anticipated. Taking into account the addition of Finland, the addition of CPRD Aurum, and the extension of the study period (end of 2020 for Sweden and Finland, end of 2021 for CPRD), a total of approximately 67,490 empagliflozin users are expected to be eligible for inclusion in the study ([Table 6](#)). However, the number of patients available for analysis may be lower. Given the observed patient numbers, it is expected that the maximum achievable matching ratios will be 1:3 for UK CPRD (GOLD and Aurum), 1:1 for Sweden, and 1:2 for Finland.

Table 6

Observed and expected number of patients eligible for inclusion in the study population, by study drug group (including fixed-dose combinations with metformin), by study country and overall, using an arithmetic growth assumption.

Year	Study drug group	Finland	Sweden	CPRD GOLD	CPRD Aurum ⁴	Pooled
2014 ¹	Empagliflozin	0	0	5		5
	DPP 4-inhibitors	5,824	3,214	2,555		11,593
	Other SGLT-2 inhibitors	127	662	683		1,472
2015 ¹	Empagliflozin	91	629	157		877
	DPP 4-inhibitors	14,130	10,305	6,851		31,286
	Other SGLT-2 inhibitors	320	1,537	2,065		3,922
2016 ¹	Empagliflozin	2,201	2,181	897		5,279
	DPP 4-inhibitors	11,391	12,126	5,648		29,165
	Other SGLT-2 inhibitors	1,463	1,183	1,740		4,386
2017 ¹	Empagliflozin	3,725	4,811	1,391		9,927
	DPP 4-inhibitors	7,402	13,677	4,577		25,656
	Other SGLT-2 inhibitors	1,475	1,191	1,493		4,159
2018 ¹	Empagliflozin	4,293	8,738	1,536		14,567
	DPP 4-inhibitors	6,959	12,798	4,158		23,915
	Other SGLT-2 inhibitors	1,610	1,030	1,470		4,110
2019 ¹	Empagliflozin	5,182	10,169	1,846		17,197
	DPP 4-inhibitors	6,158	11,673	3,622		21,453
	Other SGLT-2 inhibitors	1,853	1,061	1,665		4,579
2020 ²	Empagliflozin	2,777	5,806	1,541		10,124
	DPP 4-inhibitors	2,215	4,688	2,210		9,113
	Other SGLT-2 inhibitors	1,201	653	1,369		3,223
2021 ³	Empagliflozin			969		
	DPP 4-inhibitors			1,051		
	Other SGLT-2 inhibitors			726		
Total	Empagliflozin	18,269	32,334	8,342	8,545	67,490
	DPP 4-inhibitors	54,079	68,481	30,672	59,283	212,515

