Emigration from the study country	Censoring of follow-up time occurs at the date of emigration from the study country. Applied in all analyses.	UK: CPRD-GOLD and Aurum Sweden: Total population register ¹ Finland: Population register centre
Patient transfer	Censoring of follow-up time occurs at the date of patient transfer. Applied in all analyses.	UK: CPRD-GOLD and Aurum Sweden: NA Finland: NA
Incidence of any cancer during follow-up	A registered diagnosis of any cancer (excluding non-melanoma skin cancer) during follow-up. (ICD-10, ICD-7, ICD-O-3 and READ diagnosis codes in Annex I) Applied in all analyses.	UK: CPRD-GOLD and Aurum Sweden: Swedish cancer registry (SCR) Finland: FCR
Diabetes diagnosis other than type 2	A diagnosis of type 1 diabetes or other non-type 2 diabetes during follow-up identified using the same algorithm as used for the exclusion criteria (Section 4.2.4) Relevant ICD-10 codes and READ diagnosis codes are provided in Annex I. Applied in all analyses.	UK: CPRD and Aurum Sweden: NDR, NPR Finland: reimbursement registry
End of study period	Censoring of follow-up time occurs at end of study date i.e. 31 December 2020 (2021 for UK-CPRD). Applied in all analyses.	NA

Proprietary confidential information © 2024 Boehringer Ingelheim International GmbH or one or more of its affiliated companies

Treatment discontinuation (AT exposure- main analysis)	Censoring of follow-up time occurs 90 days after 
 - last day of medication (i.e. stop date) - new prescription of the other study drug or of a SGLT-2 inhibitor Applied only in analyses using the AT exposure definition.	UK: CPRD-GOLD and Aurum Sweden: SPDR Finland: FPR
Treatment discontinuation (AT exposure- sensitivity analysis)	Censoring of follow-up time occurs 180 days after 
 - last day of medication (i.e. stop date) - new prescription of the other study drug or of a SGLT-2 inhibitor Applied only in the sensitivity analysis using the AT exposure definition.	UK: CPRD-GOLD and Aurum Sweden: SPDR Finland: FPR

¹ The National patient register will be used if data on immigration/emigration are unavailable from the Total population register.

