6. PLANNED ANALYSIS

6.1. SUMMARY OF STUDY POPULATION IDENTIFICATION

The identification process used to identify the study populations and subgroups will be summarised using population flowcharts including the following information:

- The total number of patients in the source population.
- The number and proportion of patients not meeting inclusion criteria.
- The number and proportion of patients meeting inclusion criteria.
- The number and proportion of patients excluded after applying exclusion criteria.

Proprietary confidential information © 2024 Boehringer Ingelheim International GmbH or one or more of its affiliated companies

- The number and proportion of patients included in the study after applying inclusion and exclusion criteria [total study population].
- The number and proportion of patients using empagliflozin (out of total study population) at index date.
- The number and proportion of patients using DPP-4 inhibitors (out of total study population) at index date.

For each of the study countries, a population flowchart similar to Figure 2 will be presented.

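### Cumulative dose and duration cut-points are set on a study population that includes DPP-4 initiators, so the four planned empagliflozin exposure levels cannot all be populated

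*SAP*

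**What the plan says.** SAP Table 6 (5.1.8) defines two time-dependent exposures, cumulative dose and cumulative duration, for secondary objectives (a) and (c). The dose levels are listed as "Never 0 - <cumulative dose Q1 ≥ Q1 to < Q2 ≥ Q2 to < Q3 ≥ Q3", and duration has the same structure. Footnote 1 gives the rule for dose: "The categories are defined based on the quartiles of overall cumulative dose (grams) of the study population". Footnote 2 gives it for duration: "The categories are defined based on the quartiles of overall cumulative exposure duration (months) of the study population".

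SAP 6.1 shows who is in the study population. Both drug groups are counted out of it, and for the comparator the flowchart reports "The number and proportion of patients using DPP-4 inhibitors (out of total study population) at index date".

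Comparator patients bring almost no empagliflozin exposure. Protocol 8.2.5 excludes "Use of any SGLT-2 inhibitor or any DPP-4 inhibitor (including free and fixed-dose combinations) recorded at any time prior to index date". In the as-treated analysis, SAP Table 4 censors follow-up 90 days after a "new prescription of the other study drug or of a SGLT-2 inhibitor".

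SAP Table 16 runs the dose and duration hazard ratio models in the matched cohorts and then meta-analyses them. It confines two secondary incidence-rate analyses (daily dose and duration) to empagliflozin users, but says nothing there about cut-points. No section limits the quartiles to users.

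**The concern.** Never is already a separate level, yet the footnotes leave the never-users in the distribution that is cut. If most or half of that distribution is zero, Q1 and Q2 are zero, and the levels from 0 to below Q1 and from Q1 to below Q2 contain nobody.

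Secondary objectives (a) and (c) depend on comparing risk across rising levels. The shells in SAP Tables 26, 28, 30 and 32 have four quartile rows below the never-exposed row. SAP section 10 requires the quality-control statistician to confirm both that the analysis follows the plan and that the output matches the shells. Under the footnotes as written, both cannot be met. Someone would then choose new cut-points after the data are in hand, which a safety study should avoid for its dose-response analysis.

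**Working it through.** **Inputs.** Protocol Table 6 gives expected eligible initiators by country. The protocol states that "a total of approximately 67,490 empagliflozin users are expected to be eligible for inclusion in the study". The country columns reproduce this: 18,269 + 32,334 + 8,342 + 8,545 = 67,490. For DPP-4 inhibitors, 54,079 + 68,481 + 30,672 + 59,283 = 212,515, as printed. The expected matching ratios (Protocol 8.5) are 1:3 in the UK, 1:1 in Sweden and 1:2 in Finland. The documents print no cut-point values, so there is none to reproduce.

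**Formula.** Let z be the share of the population with zero exposure and u = 1 − z the share of users. The p-th quantile is zero whenever z ≥ p. Otherwise the share of users below it is (p − z)/u. This does not depend on the shape of the dose or duration distribution.

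**Unmatched population (the literal reading of SAP 6.1).**

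- UK: z = 89,955/(16,887 + 89,955) = 84.2%. Q1, Q2 and Q3 are all zero.
- Finland: z = 54,079/(18,269 + 54,079) = 74.7%. Q1 = Q2 = 0. Users below Q3: (0.75 − 0.7475)/0.2525 = 1.0%.
- Sweden: z = 68,481/(32,334 + 68,481) = 67.9%. Q1 = Q2 = 0. Users below Q3: (0.75 − 0.6793)/0.3207 = 22.1%.

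**Matched cohorts (the set used for the models).** At ratio 1:r, z = r/(1 + r), so the share of users below Q3 is 0.75(1 + r) − r = 0.75 − 0.25r for r from 1 to 3. Q2 is zero for any r of 1 or more.

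| Country | Unmatched: <Q1 / Q1–Q2 / Q2–Q3 / ≥Q3 | Matched, expected ratio |
|---|---|---|
| UK | 0 / 0 / 0 / 100% | 1:3: 0 / 0 / 0 / 100% |
| Finland | 0 / 0 / 1 / 99% | 1:2: 0 / 0 / 25 / 75% |
| Sweden | 0 / 0 / 22 / 78% | 1:1: 0 / 0 / 50 / 50% |

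The shares place each user by total exposure. In Sweden at exactly 1:1, Q2 sits on the zero boundary.

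**Could switchers rescue Q2?** For Q2 to exceed zero, more than half the population needs some empagliflozin exposure. The share of DPP-4 initiators who would have to start empagliflozin before the end of follow-up is (0.5N − E)/D, where N is the population, E the users and D the DPP-4 initiators.

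- Unmatched: Sweden (50,407.5 − 32,334)/68,481 = 26%; Finland (36,174 − 18,269)/54,079 = 33%; UK (53,421 − 16,887)/89,955 = 41%.
- Matched: UK 1:3, 16,887/50,661 = 33%; Finland 1:2, 9,134.5/36,538 = 25%; Sweden 1:1, none, because it is already at the boundary.

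**Pooling.** Protocol 8.7.1.4 meta-analyses only where all three countries supply an estimate. The UK supplies only the level at or above Q3, so only that level can be pooled. In the matched cohorts it holds all UK users, 75% of Finnish users and 50% of Swedish users, which is not the same contrast in each country.

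**The case against.** The strongest reply is that the intent is plain. A separate Never level and a lowest level running from zero to below Q1 make sense only if non-users were set aside first, and the shells repeat that layout. A programmer would meet an impossible zero-to-below-zero level on the first run. This stands as evidence of intent: user-only quartiles were probably meant. It does not remove the contradiction, because the footnotes state a different population, and the choice between initiators, matched initiators and exposed person-time would still be made late.

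A reader might go further and infer that no dose or duration trend could be seen in any country. The documents do not support that. The models run in matched cohorts, where Finland and Sweden keep Never plus two populated exposed levels. Those two countries supply 50,603 of the 67,490 expected users (75%). The exposures are also time-updated, so one user can contribute time to both levels. Full collapse is confined to the UK, and there only if nearly every user finds three matches: at an average ratio of 2.8, 0.75 − 0.25 × 2.8 = 5% of users would lie below Q3.

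It is also fair that never-users are half, not most, of a 1:1 Swedish cohort, and that DPP-4 initiators who switch can accrue up to 90 days of exposure. Unequal losses in the 6-month latency period could move the Swedish Q2 slightly above zero. None of this makes Q1 positive: in the 1:1 cohort that would need half of the DPP-4 initiators to have taken empagliflozin, and more elsewhere.

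**Conclusion.** The point holds as a specification error in two footnotes. As written, they give Q1 = Q2 = 0 in every unmatched country cohort, and in the matched cohorts at the expected ratios, with Sweden on the boundary. The four planned exposed levels cannot be populated: the gradient is lost in the UK, Finland and Sweden keep two exposed levels, and only the top level is available for pooling.

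The sizes rest on projected initiator counts taken before latency exclusions and as-treated censoring, with the CPRD Aurum counts extrapolated. The UK count of 16,887 comes from Protocol Table 6. The power tables use 16,360, which gives a user share of 16,360/(16,360 + 89,955) = 15.4% instead of 15.8% and changes nothing. Matching is variable up to 1:3, so realised ratios will shift the matched splits along 0.75 − 0.25r.

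The documents do not show that the analysis will be run this way, only that the written rule would produce this result. The primary objectives and secondary objective (b), daily dose, are unaffected.

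**What to change.** Amend footnotes 1 and 2 of SAP Table 6 so that the quartiles, or fixed cut-points, are derived among empagliflozin initiators in the matched analysis set only. Keep Never (the DPP-4 cohort) as the reference, outside the calculation.

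State also that the same cut-points apply in all countries, so that each pooled hazard ratio compares like with like. SAP section 3 records that individual data from Finland and Sweden cannot be pooled. Common values would therefore have to be fixed in advance, or set by a stated rule from country summaries of users' exposure, before outcomes are examined by level. Country-specific user quartiles would put 25% of users in each level by construction. Common cut-points will give shares that differ somewhat from 25% by country, which is an acceptable price for levels that can be pooled.

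The cost is two footnotes and one added sentence. No new data are needed, and the table shells stay as they are.
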